5.2 Study Procedures

5.2.1 Pre-study Procedures

Pre-study procedures must take place no more than 14 days prior to the first dose of decitabine except where noted below.

1. Bone marrow aspirate and biopsy. Standard bone marrow procurement procedures will be followed for collection of the tissue. Assessments performed on bone marrow will include correlative studies (collected under HRPO# 201011766), morphologic assessment, cytogenetics, and FISH.
2. Bone marrow or peripheral blood for flow cytometry
3. Skin biopsy sample (collected under HRPO# 201011766). There is no required time frame for this sample; it may have been collected months or even years prior to the first dose of decitabine.

5.2.2 Baseline Evaluation

Baseline evaluations must take place no more than 7 days prior to the first dose of decitabine.

1. Medical history
2. Physical exam including height, weight, and ECOG performance score.
3. Record transfusion requirements for 8 weeks before first dose of study drug
4. CBC with differential and platelets
5. Serum chemistries, including bicarbonate, calcium, glucose, total protein, albumin, BUN, potassium, chloride, sodium, creatinine, total bilirubin, AST, ALT, alkaline phosphatase, LDH
6. Urine β HCG pregnancy test if appropriate
7. Clinical pathology should be carefully reviewed to rule-out acute promyelocytic leukemia (M3-AML), and discussion between the pathologist and treating physician should take place if warranted by morphology or immunophenotype.

5.2.3 Day 1 of Each Cycle

1. Physical exam, including weight
2. CBC with differential and platelets
3. Serum chemistries, including bicarbonate, calcium, glucose, total protein, albumin, BUN, potassium, chloride, sodium, creatinine, total bilirubin, AST, ALT, alkaline phosphatase, LDH

5.2.4 Cycle 1 Days 1-10

Decitabine administration, 20 mg/m² per day given as a 1-hour continuous intravenous infusion. The dose will be calculated based on actual patient weight at

the beginning of each cycle. Patients may be premedicated with lorazepam, prochlorperazine, palonosetron, or ondansetron at the treating physician's discretion.

The clinical research coordinator should monitor for final FISH results to confirm that PML/RARA screening is negative.

5.2.5 Cycle 1 Day 10 ± 1

Bone marrow aspirate and biopsy. Standard bone marrow procurement procedures will be followed for collection of the tissue. Assessments performed on bone marrow will include correlative studies (collected under HRPO# 201011766), morphologic assessment, cytogenetics, and FISH.

5.2.6 Weekly

CBC with differential and platelets. After the first cycle, this may be changed to every other week at the discretion of the treating physician.

5.2.7 Every Other Week

Serum chemistries, including bicarbonate, calcium, glucose, total protein, albumin, BUN, potassium, chloride, sodium, creatinine, total bilirubin, AST, ALT, alkaline phosphatase, LDH. After the first cycle, this may be changed to every month at the discretion of the treating physician.

5.2.8 Cycles 1, 2, 4 and 6 Day 28 ± 4 days

Bone marrow aspirate and biopsy. Standard bone marrow procurement procedures will be followed for collection of the tissue. Assessments performed on bone marrow will include: correlative studies (collected under HRPO# 201011766), morphologic assessment, cytogenetics, and FISH.

Patients who achieve with clinical response (CRi or better) and are receiving cycles every 6 weeks, will undergo bone marrow biopsies on day 42 ± 4.

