1.3 Correlative Studies

All correlative studies will be collected under HRPO# 201011766 (“Tissue Acquisition for Analysis of Genetic Progression Factors in Hematologic Diseases”) that all patients will be concurrently enrolled in. The goals of the correlative studies include:

1. To correlate patient-specific mutations with response to decitabine.
We will perform exome sequencing of each patient’s pre-study bone marrow sample and skin sample. We will determine AML/MDS-associated variants found in the bone marrow, but not skin sample. We will correlate the presence of mutations with response (especially mutations in *DNMT3A*, *IDH1*, *IDH2*, and *TET2*). This study is powered to identify mutations with >80% sensitivity to predict decitabine response if used as a clinical assay.
2. To correlate the velocity and depth of response with response to decitabine.
We will assess tumor burden by allele frequency of patient-specific mutations in bone marrow samples collected pre study, Cycle 1 Day 10±1, Cycle 1 Day 28±4, and Cycle 2 Day 28±4. We will assess mutations in at least 24 recurrently mutated genes (including, but not limited to: *FLT3*, *DNMT3A*, *NPM1*, *TET2*, *WT1*, *IDH1*, *IDH2*, *RUNX1*, *NRAS*, *TP53*, *U2AF1*, *KRAS*, *PHF6*, *MSTP9*, *PTPN11*, *KIT*, *SMC3*, *PRUNE2*, *ETV6*, *CEBPA*, *SMC1A*, *ASXL1*, *STAG2*, *RAD21*) as well as all patient-specific mutations discovered during exome sequencing. The leukemic allele frequency will be measured using the Illumina MySeq or HiSeq platform using DNA capture by gene specific biotinylated-oligonucleotides. Patient bone marrow samples will be assessed pre-study, Cycle 1 Day 10 ± 1, Cycle 1 Day 28 ± 4, and Cycle 2 Day 28 ± 4 and compared with patient specific skin samples (normal control). The velocity of response will be calculated as the natural log rate of patient-specific mutation allele frequency clearance. Depth of response will be defined as the lowest patient-specific mutation

allele frequency in a bone marrow sample. The velocity and depth of tumor response will be correlated to:

- Achievement of clinical CR,
- Time to best response,
- Mutational status,
- Time to disease progression.

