5.0 INVESTIGATIONAL PLAN

5.1 Summary of Study Design

This is an open-label, single-arm, Phase II, biomarker study of patients with AML or MDS who are treated with 10 consecutive days of decitabine. FAB-M3 AML is excluded from this trial, because other well-tolerated options exist for the treatment of FAB-M3 acute promyelocytic leukemia. AML patients who are < 60 years old and have not received cytotoxic induction chemotherapy are also excluded, because cytotoxic therapy offers a curative possibility for these patients. MDS patients without cytopenias are also excluded because these patients can be followed with watchful-waiting.

All patients will undergo bone marrow biopsies pre-study, on Cycle 1 Day 10 \pm 1, and on Day 28 \pm 4 of Cycles 1, 2, 4, and 6. Following Cycle 6, bone marrow biopsies should be performed at the discretion of the treating physician to assess for relapse or progression. Patients will provide a skin biopsy sample pre-study. See Section 8.0 for details on correlative studies.

Patients will receive decitabine 20 mg/m²/day as a 1-hour infusion on consecutive Days 1-10 in 28-day cycles. The dose will be calculated based on actual patient weight at the beginning of each cycle.

Once AML patients achieve morphologic complete remission with incomplete blood count recovery (CRi) or MDS patients achieve a marrow complete response (Marrow CR) as defined in Section 9.0, decitabine administration may be decreased to 20 mg/m²/day for ten consecutive days every 6 weeks, to limit myelosuppressive toxicity and improve count recovery. After 2 cycles at 6 week intervals, the dose may be reduce to 20 mg/m²/day for five consecutive days in 6 week cycles, at the discretion of the treating physician. After two cycles of five consecutive days of treatment, if the patient meets the definition of CR with complete cytogenetic response as defined in Section 9.0, administration may further be decreased to three consecutive days per cycle at the discretion of the treating physician.

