6.3 Modification in Dose or Schedule for Treatment Response

Once AML patients achieve morphologic complete remission with incomplete blood count recovery (CRi) or MDS patients achieve a marrow complete response (Marrow CR) as defined in Section 9.0, decitabine administration may be decreased to 20 mg/m²/day for ten consecutive days, and the cycles may be administered every 6 weeks to limit myelosuppressive toxicity, at the discretion of the treating physician. After two cycles at six week intervals, the dose may be reduced to 20 mg/m²/day for five consecutive days of treatment in six week intervals. If the patient meets the definition of CR with complete cytogenetic response as defined in Section 9.0, administration may further be decreased to three consecutive days per cycle at the discretion of the treating physician.

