14.2.3 Secondary Endpoint Analyses

The overall response rate (CR/CRi/PR) and complete response rate (CR/CRi) will be compared with historical controls[2], and the 95% confidence intervals will be provided.

The rate of patient specific mutation clearance after 10, 28, and 56 days of therapy will be determined using an Illumina based platform. We will compare the rate of mutation clearance between the patients who achieve a CR/CRi after 4 cycles and those who do not. We anticipate that we will identify between 6 and 25 exonic SNVs per case (the range obtained with >200 AML samples sequenced to date with whole genome or exome sequencing), and that the expected 95% confidence interval of the mean variant allele frequency will be $\pm 2.56\%$ and $\pm 1.25\%$,

respectively, if we assume an anticipated standard deviation of 3.2% within the same clone. The change of tumor burden over time and its association with clinical response will be assessed using 2-way ANOVA for repeated measurement data, followed by the ad-hoc multiple comparisons for between-group differences (e.g., responders vs. non-responders) at given time points as well as the between-time differences within each group. The resultant critical P values will also be corrected using permutation analysis for multiple testing.

The percent decrease in bone marrow methylcytosine will be calculated on day 10 ± 1 . We will compare this reduction with previously published data and between the patients who achieve CR/CRi and those who do not. The correlation of peak plasma levels of decitabine with response will be assessed using 2-sample t-test or Mann-Whitney non-parametric rank-sum test as appropriate. The change of total bone marrow DNA methylcytosine from baseline and its association with both steady-state plasma drug levels and response will be assessed using 2-way ANOVA for repeated measurement data, followed by the ad-hoc multiple comparisons for between-group differences (e.g., responders vs. non-responders) and between-time differences. Similar analyses will be performed for the correlation of expression profiles and SNP analysis with pharmacokinetic data.

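### The optional response-triggered 6-week schedule can put an early responder's Cycle 2 marrow at day 70 or 84, but Section 14.2.3 analyses clearance only at nominal days 10, 28 and 56

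*Combined protocol and SAP*

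**What the plan says.** Section 5.1 sets treatment on "consecutive Days 1-10 in 28-day cycles". Once CRi (AML) or Marrow CR (MDS) is reached, Section 6.3 says "the cycles may be administered every 6 weeks to limit myelosuppressive toxicity, at the discretion of the treating physician". Neither section states a minimum number of cycles before this change. The first Day 28 marrow is in Cycle 1, so a response can be on record before Cycle 2 begins.

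Section 5.2.8 then moves the marrow: "Patients who achieve with clinical response (CRi or better) and are receiving cycles every 6 weeks, will undergo bone marrow biopsies" on day 42 ± 4. Note d of Appendix 2 repeats this and includes the correlative studies at every time point, so the research sample moves as well. Sections 1.3, 8.0 and 9.3 keep Day 28 ± 4 of Cycle 2 and give no exception.

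On analysis, Section 14.2.3 says: "The rate of patient specific mutation clearance after 10, 28, and 56 days of therapy will be determined using an Illumina based platform", and "We will compare the rate of mutation clearance between the patients who achieve a CR/CRi after 4 cycles and those who do not". The method is a repeated-measures ANOVA followed by tests of "between-group differences (e.g., responders vs. non-responders) at given time points as well as the between-time differences within each group". Section 1.3 defines velocity as a natural log rate without saying whether days are actual or nominal. It adds: "Depth of response will be defined as the lowest patient-specific mutation" allele frequency in a marrow sample, with no reference to when that sample was taken.

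**The concern.** Velocity and depth of mutation clearance are a named secondary objective (Section 2.2). A time-point contrast between responders and non-responders needs both groups sampled at about the same time on study. Here a scheduling rule triggered by response can delay the third sample. If clones clear at the same speed in both groups, a later sample still shows a lower VAF and gives more opportunity for a low minimum. If clones regrow in the longer interval without drug, the error runs the other way. In either case part of the contrast at the third time point would reflect timing rather than biology.

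The wording also leaves a gap for MDS. Section 6.3 gives 6-week cycles to patients in Marrow CR, but the day-42 rule names only CRi or better, and Section 9.2 has no CRi category. Their marrow day is not stated.

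**Working it through.** **Calendar.** Inputs: 28-day cycles (5.1); marrow on Day 28 ± 4 or, in 6-week cycles, day 42 ± 4 (5.2.8, Appendix 2 note d). Study day of the Cycle 2 marrow = length of Cycle 1 + marrow day within Cycle 2.

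| Interval before Cycle 2 | Marrow day in Cycle 2 | Study day | Window |
|---|---|---|---|
| 28 | 28 | 56 | 52–60 |
| 28 | 42 | 70 | 66–74 |
| 42 | 28 | 70 | 66–74 |
| 42 | 42 | 84 | 80–88 |

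The top row reproduces the plan's 56 days. The later windows do not overlap 52–60.

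**Dilution.** The share f of responders who shift is not given. Mean responder sampling day = 56 + 14f (day-70 case) or 56 + 28f (day-84 case).

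| f | Day-70 case | Day-84 case |
|---|---|---|
| 10% | 57.4 | 58.8 |
| 25% | 59.5 | 63 |
| 50% | 63 | 70 |
| 100% | 70 | 84 |

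**VAF at equal true clearance.** The documents give no half-life or baseline, so these are assumptions: baseline 40%, log-linear clearance, VAF(t) = 40 × 2^(−t/half-life).

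| Half-life (days) | Day 56 | Day 70 | Difference (points) |
|---|---|---|---|
| 10 | 0.8 | 0.3 | 0.5 |
| 14 | 2.5 | 1.25 | 1.25 |
| 28 | 10.0 | 7.1 | 2.9 |

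With baseline 20–50% and half-life 14–56 days, the range is 0.6 to 4.0 points at day 70 and 0.9 to 7.3 at day 84. These are per shifted sample; the effect on the responder mean is f times as large. For example, with a 28-day half-life and f = 25%, it is 0.25 × 2.9 = 0.7 points.

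**Scale.** Section 14.2.3 gives a 95% interval of ±2.56% with 6 variants and ±1.25% with 25. Both are reproduced: 1.96 × 3.2/√6 = 2.56 and 1.96 × 3.2/√25 = 1.25. Its power statement uses a 10-point difference with 6 or more variants. These describe a clone mean within one case, so they give a sense of scale and not the precision of the group contrast.

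**Velocity.** The rate is ln(VAF₀/VAF_t)/t. With the actual t and log-linear clearance, a later sample causes no bias. Only if 56 were used as the divisor would a shifted patient's rate be inflated, by 70/56 = 1.25 or 84/56 = 1.50.

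**Other time points.** The Cycle 1 Day 10 and Day 28 samples precede any response-triggered change, so those contrasts are largely unaffected.

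**The case against.** The strongest reply is that the rule reaches few patients and the plan does not commit to the error.

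- **Optional and early only.** The change is at the physician's discretion and affects the Cycle 2 marrow only if response is documented after Cycle 1 and acted on at once. Section 14.2.3 classes responders by CR/CRi after 4 cycles, so a patient first responding at Cycle 2 or 4 keeps a day-56 sample by schedule. This stands. A reader might infer that all responders are shifted; the documents do not support that.
- **Not one group only.** A reader might also infer that only responders are sampled late. Marrow CR is neither CR nor CRi, so read literally MDS patients in Marrow CR who go to 6-week cycles count among the non-responders. Holds for infection or organ dysfunction (6.1, 6.2) can delay Cycle 2 in anyone. This stands, but only the 6-week rule delays sampling because of response.
- **Section 8.0 may govern.** Section 5.1 sends the reader there for correlative studies, and it keeps Cycle 2 Day 28. If it governs and Cycle 2 starts on time, the sample is at day 56. Against that, Appendix 2 note d joins the day-42 rule to the correlative sample, and a stretched interval before Cycle 2 gives day 70 even under Section 8.0.
- **Section 6.1.** Its four cycles without adjustment concern cytopenia, whereas the trigger in 6.3 is response, so it is not a clear bar to an early change.
- **Velocity.** Nothing says the log rate is divided by a nominal 56 days, and the Study Calendar Form (Section 15.0) records dates. The 1.25- to 1.5-fold inflation is therefore conditional and not a feature of the plan.

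**Conclusion.** The point holds in a limited form. Where the optional 6-week schedule is used straight after Cycle 1, the Cycle 2 sample can fall at day 70, or day 84 if the interval before Cycle 2 is also stretched. Section 14.2.3 has no place for it except the 56-day time point. The third-time-point VAF contrast and the depth measure are then exposed to a timing difference tied to outcome.

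The size depends on the unstated share shifted and the assumed half-life. Relative figures would mislead: a VAF 29% to 62% lower at day 70 (half-lives of 28 and 10 days) sounds large but is 2.9 and 0.5 points here, per shifted sample. Velocity is biased only if nominal days are the divisor. The matter concerns one of three time points in a secondary objective. It merits a change because following the text as written builds in the mismatch and the remedy is cheap.

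**What to change.** 1. Reconcile Sections 1.3, 8.0 and 9.3 with 5.2.8 and Appendix 2 note d on the Cycle 2 marrow, and state what applies to MDS patients in Marrow CR. Which sampling day to use is for the sponsor to decide. No added marrow procedure is needed.
2. In Section 14.2.3, replace the nominal-time ANOVA contrast with a model of log VAF on actual days since first dose, for example a mixed model with continuous time, keeping all samples.
3. Compute velocity from actual dates. Compare depth over a common follow-up period, or adjust it for actual sampling time.
4. Add a sensitivity analysis limited to Cycle 2 samples taken on days 52–60, and present the Day 10 and Day 28 contrasts as support.

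Day-70 and day-84 samples should stay in the main analysis: dropping them would remove the earliest responders because of their outcome. The cost is amendment wording and slightly more analysis work, using dates already on the study forms. The downside is dependence on the assumed shape of the clearance curve. Because the model is on the log scale, the plan should also say how a VAF of zero is handled.

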5.2.9 End-of-Study Procedures

1. Physical exam
2. CBC with differential and platelets.
3. Serum chemistries including bicarbonate, calcium, glucose, total protein, albumin, BUN, potassium, chloride, sodium, creatinine, total bilirubin, AST, ALT, alkaline phosphatase, and LDH.
4. Bone marrow aspirate and biopsy. Standard bone marrow procurement procedures will be followed for collection of the tissue. Assessments performed on bone marrow will include morphologic assessment, cytogenetics, and FISH.

5.2.10 Post-study Follow-up

Patients are to be followed according to standard patient care procedures for 30 days following the date of the last decitabine dose to monitor for toxicity, survival, and response. Thereafter, the investigator or designee will record information on subsequent therapy, disease progression, and/or death every 6 months for 2 years after last dose of study drug or until the patient is lost to follow-up or dies.

5.3 Duration of Therapy

If at any time the constraints of this protocol are considered to be detrimental to the patient's health and/or the patient no longer wishes to continue protocol therapy, the protocol therapy should be discontinued and the reason(s) for discontinuation documented in the case report forms.

In the absence of treatment delays due to adverse events, treatment may continue indefinitely or until one of the following criteria applies:

- Documented and confirmed disease progression
- Death
- Adverse event(s) that, in the judgment of the investigator, may cause severe or permanent harm or which rule out continuation of study drug
- General or specific changes in the patient's condition render the patient unacceptable for further treatment in the judgment of the investigator
- Suspected pregnancy
- Serious non-compliance with the study protocol
- Lost to follow-up
- Patient withdraws consent
- Investigator removes the patient from study
- The Siteman Cancer Center decides to close the study

Patients who prematurely discontinue treatment for any reason will be followed as indicated in the study calendar.

5.4 Concomitant Therapy and Supportive Care Guidelines

5.4.1 Chemotherapy

Patients cannot receive any chemotherapy within 21 days of study enrollment and must have recovered from any treatment-related toxicities. However, patients may be receiving hydrea at enrollment and may continue on hydrea through Cycle 2 of decitabine. An indication for hydrea following 2 cycles of decitabine is evidence that the patient is not responding and decitabine should be discontinued. Other than decitabine, patients cannot receive chemotherapy during this trial.

5.4.2 Growth Factors

Erythroid growth factors should not be routinely administered to patients during the study.

Thrombopoietin receptor agonists should not be routinely administered to patients during the study.

Filgrastim (G-CSF) or sargramostim (GM-CSF) may be administered to patients with septic shock or febrile neutropenia at the discretion of the treating physician.

5.4.3 Transfusions

- *Packed red blood cells (RBCs) transfusion:*
RBC transfusions will be administered at the discretion of the treating physician.
- *Platelet transfusion:*
Platelet transfusions will be administered at the discretion of the treating physician

5.4.4 Prophylactic Antimicrobial Agents

Antimicrobial agents will be administered at the discretion of the treating physician. Common antimicrobial prophylaxis during cycles 1 and 2 include acyclovir, ciprofloxacin, and fluconazole.

5.4.5 Radiotherapy

Patients cannot receive radiotherapy within 14 days prior to study enrollment or while on study.

6.0 DOSE MODIFICATIONS

A criterion for discontinuation of the study is a delay of > 8 weeks between any two cycles.

6.1 Delay for Cytopenia or Infection

As cytopenias are a defining feature of AML and MDS, their presence alone does not generally warrant dose modifications or delays. Patients will receive four cycles of therapy without adjustment for any cytopenia. Following Cycle 4, dose modifications or delays for cytopenias will be made at the discretion of the investigator.

Patients with febrile neutropenia (temperature $\geq 38.5^\circ$ with ANC $< 1,000/\mu\text{l}$) or systemic infections should have treatment held until clinical resolution of the infection.

6.2 Delay for Organ Dysfunction

If renal dysfunction (creatinine $\geq 3 \times$ institutional upper limit of normal) or hepatic dysfunction (bilirubin $\geq 2.5 \text{ mg/dl}$ or ALT/AST $\geq 3 \times$ institutional upper limit of normal) occurs, therapy may not resume until the abnormalities have resolved to below the limits stated above. If renal or hepatic dysfunction occurs during a treatment course, the next dose of decitabine should be held, and serum chemistries should be checked twice per week. Decitabine can be resumed at full dose when creatinine, bilirubin, ALT and AST are below the limits listed above.

For grade 3-4 non-hematologic toxicities related to decitabine, decitabine treatment should be delayed until recovery to baseline or to grade ≤ 1 . Decitabine may be reintroduced with a 50% dose reduction, or at full dose at the discretion of the investigator.

